## **V. Definition of Study Outcomes**

## A. Primary Effectiveness Endpoint

The coprimary effectiveness endpoints are PPV and NPV of the ProLung Test. The null and alternative hypotheses for PPV is presented below.

$$H_0: PPV \leq PG_{Pos} \text{ versus } H_a: PPV \geq PG_{Pos}$$

where PPV is the estimated Positive Predictive Value and  $PG_{Pos}$  is the performance goal for the PPV developed below.

The null and alternative hypotheses for NPV is presented below.

$$H_0: NPV \leq PG_{Neg} \text{ versus } H_a: NPV \geq PG_{Neg}$$

where NPV is the estimated Negative Predictive Value and  $PG_{Neg}$  is the performance goal for the NPV developed below.

Each hypothesis above is tested with an exact binomial test. An alternative interval test will also be presented to demonstrate that the lower 95% confidence limit of the point estimate of PPV and NPV will lie above their respective performance goals.

### 1. Performance Goal Derivation and Sample Size

From the algorithm development data, the observed rate for  $PPV = 0.861$ , and for  $NPV = 0.471$ . Note that this PPV and NPV estimate are based on a prevalence of 0.74 from the algorithm development cohort. Since the prevalence of the validation cohort has a lower prevalence (approximately 0.637), the PPV will be lower and the NPV will be higher. The estimate for PPV is 0.778 and for NPV is 0.551. The performance goals will be computed based on these estimates of PPV and NPV.

Recall that the denominator of the PPV is the number of total tests that were deemed positive from the ProLung Test. Likewise, the NPV computation uses as its denominator the total number of ProLung Tests that turned out negative. In the 200 patients used in the algorithm study, there are 148 positive patients and 52 negative patients 109/200 (54.5%) were true positives (TP), 39/200 (19.5%) were false negatives (FN), 16/200 (8.0%) were false positives (FP), and 36/200 (18.0%) were true negatives (TN). In the validation study, there are 111 patients with malignant lesions and 63 patients with benign lesions. The performance goals are computed below that are achievable with this distribution of positive and negative patients.

Statistical simulation was performed to determine the power and estimates of PPV and NPV for the validation cohort. From that simulation an average  $PPV = 0.778$  and  $NPV = 0.552$ . This results in the following estimates: 78 TP, 33 FN, 22 FP, and 41 TN cases. The number of positive test results are  $TP + FP = 100$ , and the total number of negative test results is  $FN + TN = 74$ . To achieve approximately 90% power for PPV with 111 positive test results and a point estimate of 0.778 will require  $PG_{Pos} = 0.638$ . To achieve about 90% power for NPV with the 63 negative test results and a point estimate for NPV of 0.551, the  $PG_{Neg} = 0.381$ . Note that 90% power is required because the coprimary status indicates that both tests must be achieved so the power of the joint hypothesis is  $0.90 * 0.90 = 0.81$ , the usual power required for the tests. The power for the sum of PPV and NPV from the 10-simulation averaged 0.99.

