8.0 Study Analyses

8.1 Statistical Analysis Plan

Stabilization Phase

Stabilization Phase is not blinded. The malignancy or benignity status of the patients will be available as described in Section 4.0 Study Design. Algorithm stabilization will be tested by the Sponsor against prior clinical results and across study patients. In addition, in this phase, the Sponsor and Statistician may evaluate the impact of demographic, geographic and anatomical factors on the stability of the risk stratification Algorithm. Certain inter and intra patient bioconductance factors may also be evaluated for impact on Algorithm stability.

The statistical approach to the risk stratification Algorithm stabilization will be to modify the Algorithm using Optimal Data Analysis (ODA) programmed in Stata™ version 11 statistical software that allows a large number of variables at a time while treating each measurement variable independently. This will be in contrast to traditional multivariable regression that treats variables as possibly correlated, but only allows for a small number of predictor variables at a time which will also be used to optimize the Algorithm. Variable selection, cut-point determination, decision nodes, and so on, will be based on variables that provide improved discrimination and validate successfully.

After stability of the risk stratification has been confirmed by the Sponsor, the Algorithm will be locked, and further changes will not be permitted.

Validation Phase

The locked risk stratification Algorithm will be applied to the patients participating in the Validation Phase in which the Sponsor's Statistician is blinded to the actual patient diagnosis.

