## **Analysis Summary**

**Study Title:** A Multi-Center Trial of the ProLung Test (Transthoracic Bioconductance Measurement) as an Adjunct to CT Chest Scans for the Risk Stratification of Patients with Pulmonary Lesions Suspicious for Lung Cancer (Protocol PL-208)

**Primary Objective:** To demonstrate that the ProLung Test can assist in the assessment of patients presenting with indeterminant CT scans.

**Primary Endpoint:** The coprimary endpoints are the Positive Predictive Value (PPV) and Negative Predictive Value (NPV)

**Secondary Endpoints:** Co-secondary endpoints of sensitivity and specificity of the ProLung Test and the sum of PPV and NPV

**Additional Endpoints:** Additional Effectiveness Endpoint Analyses - Subgroup Analyses of NPV, PPV, sensitivity and specificity.

**Patient Population:** Males and females aged 18 years and older with a CT scan of the lungs that indicates one or more nodules or lesions suspicious for lung cancer.

**Study Design:** A single arm multicenter study of subjects with CT scans with nodules of undetermined significance and known diagnosis to be used to validate the ProLung Test to stratify the positive risk of lung cancer.

**Number of Patients:** 174 subjects with paired ProLung test result and a biopsy or radiological stability diagnosis for lung cancer.

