## **III. Analysis Objectives**

The primary Study hypothesis is that the ProLung Test will demonstrate safety and effectiveness in the PPV and NPV of patients with pulmonary lesions identified by CT that are suspicious for lung cancer. A statistically significant result will indicate that patients with a positive ProLung Test result will have a clinically relevant PPV.

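### The PPV and NPV goals sit at or just above the values of an uninformative test and have no clinical rationale, so passing cannot establish a clinically relevant PPV; the stated joint power of 0.81 is also wrong

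*SAP*

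**What the plan says.** SAP V.A.1 takes the outcome totals of the validation cohort as known: "In the validation study, there are 111 patients with malignant lesions and 63 patients with benign lesions". It moves the PPV and NPV expected from algorithm development to that cohort's prevalence ("Since the prevalence of the validation cohort has a lower prevalence (approximately 0.637), the PPV will be lower and the NPV will be higher"), arriving at 0.778 and 0.551. It then looks for goals that can be met: "The performance goals are computed below that are achievable with this distribution of positive and negative patients". The results are 0.638 for PPV, said to have about 90% power with 111 positive test results, and 0.381 for NPV, said to have about 90% power with 63 negative ones. The same paragraph gives the expected table as 78 TP, 33 FN, 22 FP and 41 TN, that is, 100 positive and 74 negative tests. On joint power it says that "both tests must be achieved so the power of the joint hypothesis is" 0.90 × 0.90 = 0.81.

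SAP X.A specifies one-sided exact binomial tests at 0.025. SAP III fixes the interpretation in advance: "A statistically significant result will indicate that patients with a positive ProLung Test result will have a clinically relevant PPV".

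**The concern.** A performance goal gives a single-arm study its meaning: rejecting the null shows that the device beats that number and nothing more. If the number is what a test unrelated to diagnosis would achieve, success shows association, and any claim of clinical value needs a separate argument. The SAP supplies none, yet SAP III makes the claim.

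The power paragraph adds a second problem. It uses the numbers of malignant and benign patients as denominators for PPV and NPV, although it has just said that those denominators are the numbers of positive and negative tests. The two 90% figures and their product depend on this. A reader would take the study to have 81% power for the joint claim when, on the SAP's own model, it has less.

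**Working it through.** **Inputs (SAP V.A.1 and X.A).** 111 malignant, 63 benign, n = 174; expected PPV 0.778 and NPV 0.551; expected table 78/33/22/41; goals 0.638 and 0.381; exact binomial tests, one-sided 0.025.

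**1. Uninformative values.** If the result is unrelated to diagnosis, PPV equals prevalence and NPV equals 1 − prevalence.
- PPV: 111/174 = 0.638. The goal is 0.638, a difference of 0.000.
- NPV: 63/174 = 0.362. The goal is 0.381, a difference of 0.019.

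The goals sum to 1.019, and the relative risk they imply is 0.638/(1 − 0.381) = 0.638/0.619 = 1.03. The co-primary pair therefore tests nearly the same null as the secondary test of PPV + NPV > 1 (SAP V.B) and the protocol's relative risk of 1.0 (Protocol 8.1).

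**2. What a pass looks like.** The pass mark is the smallest r with P(X ≥ r | n, goal) ≤ 0.025.
- PPV, n = 100: r = 74 (p = 0.0199; 73 gives 0.033). Exact lower limit 0.643.
- NPV, n = 74: r = 37 (p = 0.0246; 36 gives 0.041). Exact lower limit 0.381. Against 0.362 the mark would be 36, so the margin above chance is worth one patient.

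With 100 positive tests and the 111/63 split, the just-passing table is 74 TP, 26 FP, 37 FN, 37 TN. Sensitivity is 74/111 = 66.7%, specificity 37/63 = 58.7%, and 37 of 74 test-negative patients (50%) have cancer.

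**3. The SAP's marginal power.** Normal approximation: power = Φ{[(p1 − p0)√n − 1.96√(p0(1 − p0))] / √(p1(1 − p1))}. Exact: P(X ≥ r | n, p1).

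| Test | n | Pass mark | Normal | Exact |
|---|---|---|---|---|
| PPV, 0.638 vs 0.778 | 111 (SAP) | 82 | 0.900 | 0.866 |
| PPV, 0.638 vs 0.778 | 100 | 74 | 0.865 | 0.849 |
| NPV, 0.381 vs 0.551 | 63 (SAP) | 33 | 0.788 | 0.713 |
| NPV, 0.381 vs 0.551 | 74 | 37 | 0.848 | 0.841 |

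The PPV figure reproduces only with the wrong denominator and the normal approximation. The NPV figure does not reproduce: solving for 90% power at n = 63 gives a goal of about 0.35, below the uninformative 0.362.

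**4. Joint power.** Simulation (200,000 runs) at sensitivity 78/111 and specificity 41/63, with exact tests:

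| Diagnosis totals | PPV | NPV | Both | Correlation of PPV and NPV | Same verdict |
|---|---|---|---|---|---|
| Random, n = 174 | 0.855 | 0.824 | 0.70 | 0.00 | 73% |
| Fixed at 111/63 | 0.930 | 0.910 | 0.90 | 0.78 | about 97% |

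In the random case the product rule works (0.855 × 0.824 = 0.70), but the marginal powers are below 0.90. In the fixed case the marginal powers reach 0.90, but the product rule fails because the results are correlated.

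**5. An uninformative test.** With 50%, 57.5% or 70% of tests positive regardless of diagnosis, it passes both tests in under 0.1% of simulated trials.

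**The case against.** A null at the chance level is not in itself a defect. The protocol's own primary null is a relative risk of 1.0, and a useless test would almost never pass both co-primary tests. That stands: success would be sound evidence of association. Because both tests must pass, dependence between them does not inflate the type I error. If the diagnosis totals are taken as fixed, 0.81 understates the joint power.

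Three stronger readings are tempting, and the documents do not support them.
- **That knowing the split forced the goals to the chance values.** Solving for 90% power does not by itself put a goal at the prevalence. The PPV match follows from the particular inputs (0.778, n = 111), and 0.381 does not follow from its stated inputs at all. The match is a numerical fact; the documents show no intent behind it.
- **That the co-primary pair is in effect one test.** This holds only with totals fixed at 111/63. PPV and NPV use different subjects, and the planned binomial tests condition on test counts. With random totals the correlation is zero.
- **That the blind was breached.** Protocol 8.1 says that the Sponsor's "Statistician is blinded to the actual patient diagnosis", but Protocol 3.2 allows the blind to be broken once recruitment and monitoring end. The documents do not date the SAP against that step. Only diagnosis totals appear as known; the four-cell table is presented as simulation output.

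**Conclusion.** The point holds in two parts. First, the goals have no stated clinical basis and lie at (PPV) or 0.019 above (NPV) the uninformative values for this cohort, so the conclusion written into SAP III goes beyond what the test can show. Second, the power statement is wrong. With the correct denominators and the planned exact tests, marginal power is about 0.85 and 0.84. Joint power is about 0.70 on the independent-binomial basis that the SAP's multiplication implies, and about 0.90 only if the 111/63 totals are conditioned on.

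These figures rest on the SAP's expected PPV, NPV and four-cell table. The 50% cancer rate among test-negatives belongs to the just-passing table at 100 positive and 74 negative tests and is not a forecast. The type I error of the co-primary tests is not in question.

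**What to change.** 1. In SAP III, replace the statement about clinical relevance with what rejection shows: PPV above the cohort's malignancy rate (0.638) and NPV above 0.381, where 0.362 is uninformative. Keep a claim of clinical relevance only if a clinical justification for the goals is added.
2. In SAP V.A.1, use 100 and 74 as the denominators. Restate power as about 0.85 (PPV) and 0.84 (NPV), and joint power as about 0.70, noting about 0.90 if the totals are conditioned on 111/63.
3. Report PPV minus prevalence and NPV minus (1 − prevalence) with intervals. Both terms come from the same subjects, so the interval method must allow for that, for example by resampling subjects.
4. State that the goals were set with the diagnosis totals known. If the protocol's Fisher test of relative risk is reported as well, do so in its own population (definitive biopsy within 60 days of the ProLung Test, Protocol 8.1). The SAP's completed cases also include benign diagnoses inferred from radiological stability.

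The cost is SAP wording, a corrected power paragraph and one small table, with no new patients or data. The price is a weaker headline claim and a lower stated power.

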## B. Secondary Effectiveness Endpoints

There are two secondary endpoints: the estimation of sensitivity and specificity of the ProLung Test and the statistical analysis of the sum of PPV and NPV to demonstrate that the sum exceeds unity.

The co-secondary effectiveness endpoints sensitivity and specificity of the ProLung Test. There will be no hypothesis tests of these endpoints. Each will be presented with point estimates and 95% exact binomial confidence limits.

The sum of PPV and NPV will be tested with the null and alternative hypothesis below.

$H_0: PPV+NPV \leq 1$  versus  $H_a: PPV+NPV > 1$ .

### **C. Primary Safety Endpoint**

Since the device is not used in any patient treatment decisions in this study, there is no risk to the study subjects other than non-serious skin reactions to electrode patches used in testing. Therefore, this is a non-significant risk study. However, the frequency of occurrence of any adverse events will be reported to the extent these occur in the study.

## **VI. Multiplicity**

There are two coprimary hypothesis to be tested in this study, the descriptive analysis of the secondary endpoints using statistical estimation to provide exact 95% confidence limits for sensitivity and specificity, and the hypothesis test of the sum of PPV and NPV will preserve the nominal alpha level. Using the hierarchical closed form method to control alpha inflation, allows the descriptive presentation for the co-secondary endpoints of sensitivity and specificity and can use the nominal study alpha to present two-sided 95% confidence limits and the hypothesis test of the sum at the nominal alpha level as long as both co-primary hypothesis test results in statistical significance. The coprimary endpoints must both be statistically significant so there is no alpha inflation for the two coprimary hypothesis tests.

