2.0 Study Objectives

2.1 Objectives and Aims

The primary Study hypothesis is that the ProLung Test will demonstrate safety and efficacy in the risk stratification of patients with pulmonary lesions identified by CT that are suspicious for lung cancer. A statistically significant result will indicate that patients with a high ProLung Test result have a greater risk of developing lung cancer than patients with a low test result.

There are three Specific Aims of this study:

1. Optimize and confirm the stability of the ProLung Test risk-stratification algorithm in patients with a diagnosis.
2. Externally validate the efficacy of the ProLung Test risk-stratification algorithm by comparing the test result to the conclusive patient diagnosis.
3. Assess the safety and tolerability of the ProLung Test procedures.

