## **X. Effectiveness Analyses**

### **A. Primary Effectiveness**

The data from all study sites or pseudo-sites will be pooled and the primary analysis will be done by a one-sided exact binomial test of the performance goal for PPV and NPV with nominal P-value of 0.025. Alternatively, the lower one-sided 97.5% confidence limit for PPV and NPV will be computed and compared to each performance goal. If these limits both are greater than the performance goal, then the null hypothesis will be rejected.

An exploratory descriptive analysis will be provided for PPV and NPV by study site or pseudo-site. The point estimates and 95% two-sided confidence limits will be presented by study site or pseudo-site. Recall that because no site was intended to have adequate power for the primary endpoint, this analysis is unlikely to show that by-site lower confidence limit for PPV and NPV will be above the performance goals.

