### **B. Secondary Effectiveness**

The first secondary endpoints, co-secondary endpoints of sensitivity and specificity of the ProLung Test will be estimated. Sensitivity is defined as the proportion of subjects with ProLung Tests that are positive among subjects with positive biopsy results. Specificity is defined as the proportion of subjects with ProLung tests that are negative among the subjects with a negative biopsy or CT follow-up result. Each of these endpoints will be estimated from the data and presented with their 95% exact confidence intervals.

The second secondary endpoint the test of the sum of PPV and NPV will be tested with a continuity corrected z-statistic presented below. An estimate is needed for the standard error of the sum of PPV and NPV, because PPV and NPV are unlikely to have equal variances, the standard error of the sum can be estimated by the following expression for linear combinations of items that have unequal variances.

$$SE(PPV + NPV) = \sqrt{\frac{PPV(1-PPV)}{TP+FP} + \frac{NPV(1-NPV)}{TN+FN} + \rho \sqrt{\frac{PPV(1-PPV)}{TP+FP}} \sqrt{\frac{NPV(1-NPV)}{TN+FN}}}$$

where TP is the number of true positives, FP is the number of false positives, TN is the number of true negatives, FN is the number of false negatives, and  $\rho$  is the estimate of the correlation coefficient between PPV and NPV. Note that the PPV has a negative correlation with NPV so  $\rho$  is negative reducing the standard error than if PPV and NPV were independent.

The test statistic is given by the formula below.

$$Z = \frac{(PPV+NPV - \frac{1}{2}(\frac{1}{TP+FP} + \frac{1}{TN+FN}) - 1)}{SE(PPV+NPV)}$$

If  $Z > 1.96$  ( $P < 0.025$ ), then the sum of PPV and NPV will be considered to be greater than unity. Alternatively, if the lower one-sided 97.5% confidence limit of the sum is greater than 1, the null hypothesis will be rejected. The lower confidence limit is computed by the formula below:

$$LCL_{0.975} = (PPV + NPV) - 1.96 * SE(PPV + NPV).$$

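### The 0.99 power stated for the PPV+NPV > 1 test is unconditional, but the SAP runs that test only after both co-primaries succeed, when it can no longer fail

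*SAP*

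**What the plan says.** SAP section V.A makes PPV and NPV co-primary. Section X.A tests each with a "one-sided exact binomial test of the performance goal for PPV and NPV with nominal P-value of 0.025", and section VI requires both to be significant. The performance goals in section V.A.1 are 0.638 for PPV and 0.381 for NPV.

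Section V.B adds a secondary test, described as "the statistical analysis of the sum of PPV and NPV to demonstrate that the sum exceeds unity". Section X.B gives a continuity-corrected Z. If Z is above 1.96, "then the sum of PPV and NPV will be considered to be greater than unity". Section X.B also offers an alternative rule: reject if the lower one-sided 97.5% limit of the sum, computed without the continuity correction, is above 1. The standard error contains a correlation rho that is said to be negative but is given no value.

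Section VI allows "the hypothesis test of the sum at the nominal alpha level as long as both co-primary hypothesis test results in statistical significance".

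Section V.A.1 derives joint co-primary power as 0.90 × 0.90 = 0.81 and then states: "The power for the sum of PPV and NPV from the 10-simulation averaged 0.99". It does not say whether that figure takes the precondition into account.

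**The concern.** A test that runs only after two others succeed cannot succeed more often than they do jointly. Placed beside 0.81, the 0.99 tells the reader that the sum claim is almost assured, when under section VI it is exactly as uncertain as the co-primary claim.

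The precondition also leaves the sum test with nothing to do. PPV + NPV > 1 is the same statement as PPV > 1 − NPV: cancer is more frequent among test-positive than test-negative subjects. That is the association in Protocol 2.1 ("A statistically significant result will indicate that patients with a high ProLung Test result have a greater risk"). If both co-primaries succeed, it is already established. If one narrowly misses, the sum is the only formal test in the SAP that could still support it, and it may not be used.

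**Working it through.** **Inputs.** From SAP V.A.1: planning PPV 0.778 and NPV 0.551 (0.552 in the simulation); expected TP 78, FN 33, FP 22, TN 41, so 100 positive and 74 negative tests; 111 malignant and 63 benign lesions, N = 174; goals 0.638 and 0.381. From SAP X.A and X.B: one-sided 0.025 exact binomial tests, and the formulas for SE and Z. Assumption: rho = 0 unless stated, because the SAP gives no value.

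**1. Reproduce the 0.99.**
- SE = √(0.778 × 0.222/100 + 0.552 × 0.448/74) = 0.0712.
- Continuity correction = ½(1/100 + 1/74) = 0.0118.
- Z = (1.330 − 0.0118 − 1)/0.0712 = 4.47.
- Power = Φ(4.47 − 1.96) = 0.994.

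Exact enumeration with diagnoses fixed at 111/63 (sensitivity 78/111, specificity 41/63) also gives 0.994. The stated figure is right as the power of an unconditional test.

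**2. Apply the precondition.** P(sum declared) = P(both co-primaries succeed and Z > 1.96) ≤ P(both co-primaries succeed).

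| Basis | Both co-primaries | Shortfall from 0.99 |
|---|---|---|
| SAP product, 0.90 × 0.90 | 0.81 | 0.18 |
| Exact, diagnoses fixed at 111/63 | 0.90 | 0.09 |
| Exact, test results fixed at 100/74 | 0.71 | 0.28 |

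In the last row the critical counts are 74 of 100 and 37 of 74. The separate powers are 0.849 and 0.841, with product 0.714 (0.718 if NPV is 0.552). In the middle row the two estimates are positively correlated (about 0.78), so joint power is higher than the product of the separate powers, 0.930 and 0.910.

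The gap widens if accuracy is lower. With diagnoses fixed at 111/63, sensitivity/specificity of 0.68/0.62 gives 0.72 with the precondition and 0.96 without it; 0.65/0.60 gives 0.45 and 0.87.

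**3. Can the sum test fail once it is reached?** The goals add to 0.638 + 0.381 = 1.019 > 1. Every possible table with N = 174 was enumerated. Both co-primaries pass in 109,852 tables, and the sum test fails in none of them (smallest Z 2.73). A negative rho only raises Z. So the inequality in step 2 is an equality: the chance of declaring the sum is the joint co-primary power.

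**4. What the precondition protects against.** If PPV + NPV ≤ 1, at least one co-primary null is true, and by step 3 every co-primary win is also a sum win. Without the precondition, the chance of any false claim in that case is therefore the size of the sum test itself. If PPV + NPV > 1, the only possible false claim is the joint co-primary one, already held at 0.025. What matters is whether the sum test holds 0.025. For an uninformative test with 57.5% positive (sensitivity 0.575, specificity 0.425, diagnoses 111/63), its size is:

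| rho | Corrected Z | Uncorrected limit rule |
|---|---|---|
| 0 | 0.018 | 0.026 |
| −0.25 | 0.024 | 0.034 |
| −0.5 | 0.031 | 0.045 |
| −1 | 0.060 | 0.079 |

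At rho = 0 the corrected Z has size 0.015 to 0.021 for test-positive rates from 0.3 to 0.8. At an extreme rate of 0.05 it reaches 0.054.

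**The case against.** The strongest reply is that nothing here is miscalculated. The 0.99 is a valid marginal power, the SAP nowhere calls it power after the precondition, and neither the sample size nor the performance goals are shown to depend on it. Testing a secondary endpoint only after the primaries is an ordinary fixed sequence that controls error. All of this stands. What remains is that a reader of sections V.A.1 and VI together is given a power for an analysis that the plan does not run.

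The gap also depends on true accuracy. At the development cohort's sensitivity and specificity (109/148 and 36/52), joint co-primary power with 111/63 is itself 0.99. But the SAP plans on lower values and quotes its power there.

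A reader might infer more than the documents support:

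- *That the precondition gives no error control and can simply be deleted.* This holds only if the sum test is itself level 0.025. With the negative rho that section X.B describes, or with its uncorrected limit rule, the test can exceed 0.025, and the precondition currently hides that.
- *That the stated power is wrong by a settled 18 points.* That uses the SAP's independence product; by sampling model the gap is about 9 to 28 points.
- *That sensitivity and specificity intervals also depend on co-primary success.* Section VI is loosely worded, but sections V.B and X.B present them unconditionally and without tests.
- *That the precondition is what removes the protocol's hypothesis.* Protocol 8.1 tests relative risk directly with Fisher's exact test. The SAP's move to PPV and NPV goals displaced that test; section VI only limits the substitute.

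**Conclusion.** The point holds in limited form. Under section VI the probability of declaring PPV + NPV > 1 equals the joint co-primary power: 0.81 on the SAP's figure, and between about 0.71 and 0.90 by exact calculation at the planning values. The 0.99 describes an unconditional test. Once the precondition is met the sum test cannot fail at N = 174, so it adds no evidence.

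The co-primary conclusions are unaffected. The range reflects whether diagnosis counts or test-result counts are treated as fixed. The 109,852-table result uses the stated goals, exact one-sided 0.025 tests and rho = 0; a negative rho would only strengthen it. Whether to keep the precondition is a design choice, but the stated power should match the choice made.

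**What to change.** Choose one of two repairs.

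1. **Keep the precondition.** In V.A.1, replace 0.99 with the joint co-primary power, or label 0.99 as marginal, unconditional power. In VI, state that success on the sum follows from success on both co-primaries. This changes no decision rule.

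2. **Test the sum first, or unconditionally, at one-sided 0.025.** Then test both co-primaries at one-sided 0.025 each, both required. This is acceptable only with a level-0.025 test. Either set rho to 0 and make the continuity-corrected Z the sole rejection rule (size 0.018 in the planned setting), or use a one-sided Fisher exact test of the same hypothesis, which also holds its level at extreme test-positive rates. In both cases, drop the uncorrected limit as a rejection rule. Success on the sum alone should be worded as association (more cancer among high-risk subjects), not as a clinically relevant PPV.

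The first repair costs a sentence or two. The second costs a few sentences in sections VI and X.B, and should be dated before test results and diagnoses are joined. It needs no extra patients and loses no co-primary power: every co-primary win at N = 174 passes the Z test at rho = 0, and a check of the same tables found that none fails the Fisher test. Its downside is that a positive sum with a failed co-primary must be reported as a weaker claim.
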